6.2. Preparation/Handling/Storage/Accountability

- The investigator or designee must confirm appropriate temperature conditions have been maintained during transit for all study interventions received and any discrepancies are reported and resolved before use of the study intervention, as applicable for temperature-monitored shipments.
- Only maternal participants enrolled in the study may receive study intervention and only authorized site staff may supply or administer study intervention. All study interventions must be stored in a secure, environmentally controlled, and monitored (manual or automated recording) area in accordance with the labeled storage conditions with access limited to the investigator and authorized site staff. At a minimum, daily minimum and maximum temperatures for all site storage locations must be documented and available upon request. Data for nonworking days must indicate the minimum and maximum temperature since previously documented for all site storage locations upon return to business.
- The investigator, institution, or the head of the medical institution (where applicable) is responsible for study intervention accountability, reconciliation, and record maintenance (ie, receipt, reconciliation, and final disposition records). All study interventions will be accounted for using an investigational product accountability form/record.
- Further guidance and information for the final disposition of unused study interventions are provided in the investigational product manual (IP manual).
- Any storage conditions stated in the SRSD will be superseded by the storage conditions stated on the product label.

- Study interventions should be stored in their original containers and in accordance with the labels.
- See the IP manual for storage conditions of the study intervention once reconstituted.

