6.3.3. Allocation to Investigational Product

Allocation of maternal participants to vaccine groups will proceed through the use of an interactive response technology (IRT) system (interactive Web-based response [IWR]). The site personnel (study coordinator or specified designee) will be required to enter or select information including but not limited to the user's identification (ID) and password, the protocol number, and the maternal participant number. The site personnel will then be provided with a vaccine assignment, randomization number, and dispensable unit (DU) or container number as investigational product is being supplied via the IRT system. The IRT system will provide a confirmation report containing the maternal participant number, randomization number, and DU or container number assigned. The confirmation report must be stored in the site's files.

Investigational product will be dispensed at the study visits summarized in the [SoA](#).

The study-specific IRT reference manual and IP manual will provide the contact information and further details on the use of the IRT system.

Maternal participants will be assigned to receive investigational product according to the randomization scheme. Investigators will remain blinded to each maternal participant's assigned investigational product throughout the course of the study. In order to maintain this blind, an otherwise uninvolved third party will be responsible for the preparation and

dispensing of all investigational product and will endeavor to ensure that there are no differences in time taken to dispense or visual presentation following randomization.

In the event of a Quality Assurance audit, the auditor(s) will be allowed access to unblinded investigational product records at the site(s) to verify that randomization/dispensing has been done accurately.

Maternal participants will be allocated to a vaccine group as described above. The infants of the maternal participants will be assigned an infant participant number at birth.

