8.2.5. Stopping Rules – Maternal Participants

Hematology, blood chemistry, AE data, and e-diary reactogenicity data will be monitored on an ongoing basis by the investigator (or medically qualified designee) and sponsor in order to promptly identify and flag any event that potentially contributes to a stopping rule.

If it is suspected that a stopping rule has been met based on blinded safety assessment, the sponsor's designated unblinded personnel will decide whether a stopping rule has been met based on unblinded randomization information.

In the event that the unblinded sponsor personnel confirm that a stopping rule is met, the following actions will occur:

- The IRC will review all appropriate data.
- The stopping rule will PAUSE all randomization and vaccination.
- The E-DMC will be informed.
- All other routine study conduct activities including, ongoing data entry, reporting of AEs, participant e-diary completion, blood sample collection, and participant follow-up, will continue during the pause.

A stopping rule is met if any of the following events occur after administration of the investigational RSV vaccine. E-diary data confirmed by the investigator as being entered by the maternal participant in error will not contribute toward a stopping rule.

- If any RSV-vaccinated participant develops an SAE that is assessed as possibly related, or for which there is no alternative, plausible, attributable cause.
- If any RSV-vaccinated maternal participant develops a Grade 4 local reaction or systemic event within 7 days after vaccination that is assessed as possibly related by the investigator, or for which there is no alternative, plausible, attributable cause.
- If any RSV-vaccinated maternal participant develops a fever $>104.0^{\circ}\text{F}$ ($>40^{\circ}\text{C}$), within 7 days after vaccination, that lasts for at least 24 hours and is assessed as possibly related by the investigator, or for which there is no alternative, plausible, attributable cause.
- If any RSV-vaccinated maternal participant experiences any of the following within 7 days after vaccination: severe vaginal bleeding (eg, partial abruption); severe preeclampsia; eclampsia; hemolysis, elevated liver enzymes, and low platelet count (HELLP) syndrome; life-threatening sequelae of preeclampsia (eg, pulmonary edema), stillbirth, or fetal loss. Refer to the SRM for further details.

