8.3.1. Time Period and Frequency for Collecting AE and SAE Information

The time period for actively eliciting and collecting AEs and SAEs (“active collection period”) for each maternal participant including her fetus begins from the time the maternal participant provides informed consent, which is obtained before participation in the study (ie, before undergoing any study-related procedure and/or receiving investigational product), through and including a minimum of 1 month after the last administration of the investigational product.

In this study, the investigator and site staff will ensure the active elicitation and collection of AEs and SAEs through 1 month after vaccination. From 1 month after vaccination until the maternal participant completes the study, MAEs and SAEs will be collected.

For the infant participant, the time period for actively eliciting and collecting AEs and SAEs (“active collection period”) begins at birth and continues through and including a minimum

of 28 days after birth. From Visit 2 until the last study visit, only AEs of special interest, MAEs, and SAEs, including hospitalizations, will be reported.

CCI

In addition, AEs occurring up to 48 hours after blood draws CCI that are related to study procedures must be reported in the CRF.

For maternal participants who are screen failures, the active collection period ends when screen failure status is determined.

If the participant withdraws from the study and also withdraws consent for the collection of future information, the active collection period ends when consent is withdrawn.

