8.3.1.1. Reporting SAEs to Pfizer Safety

All SAEs occurring in a participant during the active collection period are reported to Pfizer Safety on the CT SAE Report Form and the Exposure During Pregnancy Supplemental Form if applicable.

If the outcome of the pregnancy meets the criteria for an SAE (ie, ectopic pregnancy, spontaneous abortion, including miscarriage and missed abortion, intrauterine fetal demise, neonatal death defined as those that occur within 1 month of birth, or congenital anomaly in a live-born baby, a terminated fetus, an intrauterine fetal demise, or a neonatal death), the investigator should follow the procedures for reporting SAEs. In addition, infant deaths after 1 month of age should be reported as SAEs.

Further follow-up may be requested by the sponsor and will be handled on a case-by-case basis (eg, follow-up on preterm infants to identify developmental delays).

SAEs occurring in a participant after the active collection period has ended are reported to Pfizer Safety if the investigator becomes aware of them; at a minimum, all SAEs that the investigator believes have at least a reasonable possibility of being related to investigational product must be reported to Pfizer Safety.

The same is applied for those SAEs after the active collection period has ended should they occur to the fetus. In addition, infant deaths that occur after 12 month of age should be reported as SAEs when the investigator believes the death has at least a reasonable possibility of being related to investigational product.

Follow-up by the investigator continues throughout and after the active collection period and until the event or its sequelae resolve or stabilize at a level acceptable to the investigator, and Pfizer concurs with that assessment.

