9.3. Populations for Analysis

For purposes of analysis, the following populations are defined for maternal and infant participants:

Population	Description
Enrolled	All maternal participants who sign the ICD.
Randomly assigned to investigational product	All maternal participants who are assigned a randomization number in the IRT system.
Evaluable - Maternal	All maternal participants who are eligible, receive the investigational product to which they were randomized, have blood drawn for assay testing within the specified time frame, have valid and determinate assay results for the proposed analysis, and have no major protocol violations.
Evaluable - Infant	All infant participants who are eligible, are born to the maternal participants who received the investigational product to which they were randomized, have blood drawn for assay testing within the specified time frame, have valid and determinate assay results for the proposed analysis, and have no major protocol violations.
Modified intent-to-treat (mITT) - Maternal	All randomized maternal participants who receive investigational product and have at least 1 valid and determinate assay result for the proposed analysis.
mITT - Infant	All infant participants who are born to vaccinated maternal participants and have at least 1 valid and determinate assay result for the proposed analysis.
Safety - Maternal	All randomized maternal participants who receive investigational product.
Safety - Infant	All infant participants who are born to vaccinated maternal participants.

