10.2.2. Hematology and Blood Chemistry

Blood samples for hematology and blood chemistry assessments (approximately 10 mL) will be collected for all maternal participants at screening (Visit 0).

Repeat testing of the protocol-required laboratory parameters is permitted to confirm results. Additional laboratory testing not specified in the protocol may be performed at the discretion of the investigator as follow-up to an AE and should be recorded in the maternal participant's source documents. The safety laboratory tests in Table 7 will be performed at times defined in the [SoA](#).

Table 7. Laboratory Tests

Hematology	Chemistry
Hemoglobin	BUN and creatinine
Hematocrit	AST, ALT
RBC count	Total bilirubin
Platelet count	Alkaline phosphatase
WBC count	
Total neutrophils (Abs)	
Eosinophils (Abs)	
Monocytes (Abs)	
Basophils (Abs)	
Lymphocytes (Abs)	

Abbreviations: Abs = absolute; ALT = alanine aminotransferase; AST = aspartate aminotransferase; BUN = blood urea nitrogen; RBC = red blood cell; WBC = white blood cell.

A toxicity grading scale adapted for use in pregnant women will be used to grade laboratory test abnormalities.²⁸

If abnormal laboratory parameters are reported at screening (Visit 0) and the investigator believes the results to be erroneous, the abnormal laboratory parameters may be retested.

10.3. Appendix 3: Adverse Events: Definitions and Procedures for Recording, Evaluating, Follow-up, and Reporting

For maternal immunization clinical studies conducted in pregnant women, data on the EDP as well as pregnancy outcome are collected and analyzed in the clinical database. For these studies, in general, EDP cases are not reportable unless associated with SAEs/nonserious AEs.

The term “participant” in this section refers to (1) the maternal participant and her fetus; and after delivery (2) the maternal participant and (3) the infant participant.

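### Read literally, the SAE pause rule does not reach live-born infants, though wider coverage may have been meant; the Protocol should name them

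*Protocol*

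**What the plan says.** Protocol Section 8.2.5 is headed for maternal participants and sets six triggers. When unblinded sponsor personnel confirm that one is met, the effect is immediate and general: "The stopping rule will PAUSE all randomization and vaccination". The IRC then reviews the data and the E-DMC is informed.

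The first trigger is the general SAE rule: "If any RSV-vaccinated participant develops an SAE that is assessed as possibly related, or for which there is no alternative, plausible, attributable cause". The other five concern maternal reactogenicity, fever, obstetric events, premature labor or rupture of membranes, and clusters of Grade 3 events.

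On who is vaccinated, Section 6.2 is plain: "Only maternal participants enrolled in the study may receive study intervention". On infants, Section 6.3.3 says: "The infants of the maternal participants will be assigned an infant participant number at birth". Section 9.3 defines the infant safety population as "All infant participants who are born to vaccinated maternal participants". The opening text of Appendix 3 (Section 10.3) says that, within that section, the word participant "refers to (1) the maternal participant and her fetus; and after delivery (2) the maternal participant and (3) the infant participant".

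**The concern.** Infant safety is one of the two primary objectives (Section 3), and Section 2.1 describes this as the first study of the vaccine in pregnant women and their infants. A possibly related SAE in a vaccinated mother meets a defined rule that stops dosing until it is reviewed. The same event in her newborn does not clearly do so.

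What is at stake is how quickly, and how predictably, dosing stops after a suspected vaccine-related harm to an infant. Section 8.2.5 asks investigators and the sponsor to flag any event that might count toward a rule. If the rule's reach is uncertain, two people reading it in good faith could act differently on the same infant SAE.

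**Working it through.** The plan gives no figure on this point, so the check sets the texts side by side.

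**Step 1. Which trigger could apply to an infant?**

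| Bullet in 8.2.5 | Says maternal? | Limit after vaccination |
|---|---|---|
| 1. Possibly related or unexplained SAE | No | None |
| 2. Grade 4 local or systemic reaction | Yes | 7 days |
| 3. Fever above 40°C for at least 24 hours | Yes | 7 days |
| 4. Severe obstetric events, stillbirth, fetal loss | Yes | 7 days |
| 5. Premature labor or rupture of membranes (2 or more women) | Yes | 14 days |
| 6. Same or similar Grade 3 AE (4 or more women) | Yes | 7 days |

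Only bullet 1 is open to infants.

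**Step 2. Does a live-born infant meet bullet 1?** It has two conditions: the person is a participant, and that participant is RSV-vaccinated. The infant meets the first (Sections 6.3.3 and 10.3). It does not meet the second, because only mothers are dosed (Section 6.2). Where the Protocol means infants, it describes them by the mother's vaccination (Section 9.3). The heading points the same way: Sections 8.2.6, 8.2.7, 8.2.9 and 8.2.10 are headed for all participants, and 8.2.5 is not. No infant stopping-rule section appears in the table of contents or the visible text.

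**Step 3. Which events are affected?**

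- *Fetal SAE before delivery.* Reasonably covered. Section 8.3.1 says the active collection period "for each maternal participant including her fetus begins from the time the maternal participant provides informed consent", and Appendix 3 groups the fetus with the mother. Bullet 4 adds stillbirth and fetal loss within 7 days, with no causality test.
- *Congenital anomaly in a live-born infant.* Arguably covered. Section 3.2 defines anomalies as arising in utero, and Section 8.3.1.1 treats them as a pregnancy outcome.
- *Neonatal death.* Less clear. Among the pregnancy outcomes that count as SAEs, Section 8.3.1.1 lists "neonatal death defined as those that occur within 1 month of birth, or congenital anomaly in a live-born baby", but nothing there refers to the pause rule.
- *Other infant SAEs arising after birth, and infant death after 1 month.* Not covered on the literal text. Infant AE collection starts separately at birth (Section 8.3.1).

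**Step 4. What other route leads to a pause?** Under Section 6.3.2, unblinded sponsor personnel outside the study team carry out ongoing safety review. Under Section 9.5.2, the E-DMC reviews safety at charter-defined intervals, may meet at other times, and may recommend a pause; the sponsor makes the final decision. The reviews are required. No infant event is defined whose occurrence compels a pause.

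**Step 5. Can it happen while dosing continues?** Vaccination is allowed up to 36 0/7 weeks (Section 5.1.1). The Protocol provides for delivery before the 2-week visit (Section 8.10.1.3), and SAP Section 6.4 has subgroups for birth within 14 and within 30 days of vaccination. Births can therefore follow soon after dosing starts. How many women would still be unvaccinated cannot be derived, because the documents give no enrollment timeline.

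**The case against.** The strongest reply is that the broader reading is the intended one. Bullet 1 alone omits the word maternal, which looks deliberate beside five bullets that include it. The rule turns on the term SAE, which is defined only in Appendix 3, and there the infant is a participant. Section 8.3.1.1 treats neonatal death and congenital anomaly as outcomes of the pregnancy, and that pregnancy is the vaccinated mother's.

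Most of this stands as evidence of intent. It does not settle the text: Appendix 3 limits its definition to its own section, it lists the infant apart from the mother after delivery, and bullet 1 still requires the participant to be RSV-vaccinated.

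A second reply is that infants are monitored in any case. That stands too, and it limits the consequence. It does not supply a defined trigger, and the maternal SAE rule exists although the same monitoring covers mothers.

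A third reply is that the IRC and E-DMC charters and the study reference manual are not among the documents, and parts of Section 8.2 are redacted. An infant trigger may sit there. This cannot be excluded, but investigators work from the Protocol, which would then need a cross-reference.

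**Conclusion.** The point holds as a defect of wording in a safety rule. Taken literally, bullet 1 does not reach live-born infants; taken with its context, it may have been meant to. A possibly related SAE in a live-born infant therefore has no unambiguous defined pause, and stopping depends on the judgement of required reviewers. The clearest case is an infant SAE arising after birth, including neonatal or later infant death.

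Three stronger inferences are not supported. The documents do not show that infants were deliberately left out. They do not show that infant safety goes unwatched. Nor do they show that a congenital anomaly triggers no pause, since it is arguably a fetal or pregnancy-outcome SAE already within the rule.

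The consequence is a possible delay in pausing. It has no numerical size: it depends on how far births overlap with continuing vaccination, and it is nil if all dosing ends before any such event. The conclusion assumes that no unseen charter, manual or redacted passage already defines an infant trigger. It is worth correcting because the change is small and protective, but it does not call the design into question.

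**What to change.** In the next protocol amendment, change the subject of bullet 1 in Section 8.2.5 to: *any RSV-vaccinated maternal participant, her fetus, or her infant (birth through the 12-month visit)*. Leave the rest of the bullet as it is, and extend the section heading to infants.

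Two things should not be added. Bullet 1 names no assessor of relatedness, unlike bullets 2, 3 and 6; inserting the investigator would mean that a sponsor assessment no longer sufficed. The clause on events with no alternative cause should apply to all infant SAEs. Restricting it to named events such as neonatal death or anomaly could leave the rule narrower than the broader reading of the present text, for example for an unexplained infant death after 1 month.

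If a charter or the study reference manual already contains an infant trigger, the Protocol should cite it and the wording should be aligned.

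The cost is one reworded bullet and a heading, plus an occasional extra pause for an infant SAE while vaccination is still ongoing. That matters somewhat in a trial whose vaccinations are timed to the RSV season. No analysis in the SAP changes.

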8.2.5.1. Enrollment and Vaccination After a Stopping Rule Is Met

Once the IRC has reviewed the safety data and has provided guidance, a notification will be sent from the sponsor to the sites with guidance on how to proceed.

8.2.6. Physical Examinations – All Participants

Maternal Participants: The physical examination will include any clinically significant abnormalities within the following body systems: general appearance; skin; head, eyes, ears, nose, and throat; heart; lungs; abdomen; musculoskeletal; extremities; neurological; and lymph nodes. Height (screening visit only) and weight will also be measured and recorded.

The obstetric examination will include, but is not limited to, scars from previous deliveries, fundal height, fetal heart tones, and fetal movement.

Investigators should pay special attention to clinical signs related to previous serious illnesses.

Infant Participants: The physical examination will include any clinically significant abnormalities within the following body systems: general appearance; skin; head, eyes, ears, nose, and throat; heart; lungs; abdomen; back; musculoskeletal; extremities; genitourinary; neurological; and lymph nodes.

Length, head circumference, and weight will also be measured and recorded.

8.2.7. Vital Signs – All Participants

Maternal Participants: Oral temperature, seated blood pressure, and heart rate will be assessed.

- Blood pressure and heart rate measurements will be assessed with a completely automated device. Manual techniques will be used only if an automated device is not available.
- Blood pressure and heart rate measurements should be preceded by at least 5 minutes of rest for the participant in a quiet setting without distractions (eg, television, cell phones).

Infant Participants: Rectal temperature, heart rate, and respiratory rate will be assessed at all visits; additionally, oxygen saturation by pulse oximetry will be assessed at Visit 1 CCI
[REDACTED] All attempts should be made to help ensure that measurements are taken while the infant is resting quietly.

- Heart rate measurements may be assessed with a completely automated device, or manual techniques may be used if an automated device is not available. If a manual technique is used, heart rate should be assessed over 1 minute.
- Oxygen saturation should be measured by pulse oximetry with a completely automated device over 1 minute and a representative value recorded.
- Respiratory rate should be assessed over 1 minute.

